13.2.1 Liver Function Tests

A matrix scatter plot of Liver Enzymes and Bilirubin will be showing the maximum ALT, AST, ALP and total bilirubin during the treatment period crossed against each other on log scales. Different dots will be used for roxadustat and placebo.

Individual displays of abnormal Liver Enzymes (AST or ALT ≥ 3 x ULN) and Bilirubin parameters (T. Bili ≥ 2 x ULN) with corresponding other liver enzymes and bilirubin values during the treatment periods will be listed.

Time to first occurrence of abnormal Liver Enzymes or Bilirubin will be plotted.

For subjects who require further liver function investigations, additional information will be collected and listed.

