4 STUDY DESIGN

4.1 Description of the Study

This is a Phase 3, multicenter, randomized, double-blind, placebo-controlled study to evaluate the safety and efficacy of roxadustat in the treatment of anemic subjects with Stage 3, 4 or 5 CKD who are not on dialysis. This study is planned to recruit up to 1200 subjects from approximately 200 study centers worldwide.

This study will consist of three study periods as follows:

- Screening Period: Up to 6 weeks
- Treatment Period: Treatment duration is variable for individual subjects. In order to complete the Treatment Period simultaneously for all study subjects, the minimum treatment duration may be less than 52 weeks, with a maximum treatment duration of up to 3 years after the last subject is randomized.
- Post-treatment Follow-Up Period*: 4 weeks
(*or enroll into an Open Label Extension study)

Refer to Appendix 3 for a diagrammatic representation of the study schema.

Following the Screening Period, subjects will be randomized in a 2:1 ratio to receive roxadustat (approximately 800 subjects) or placebo (approximately 400 subjects). Dosing will be TIW throughout the study, except in subjects who have already converted to BIW or QW dosing regimens as a result of being enrolled under previous Study FGCL-4592-060 protocol versions. Starting doses of , respectively.

Table 1. Treatment Arms

Treatment Arms	Correction	Maintenance	n (FG-4592)	n (Placebo)
1A	TIW	QW	100 ^a	0
1P	TIW	QW	0	50 ^a
2A	TIW	BIW	100	0
2P	TIW	BIW	0	50
3A	TIW	TIW	100	0
3P	TIW	TIW	0	50

Abbreviations: A = active control; BIW = twice a week; n = number of subjects; P = placebo; TIW = three times a week; QW = once a week.

^a These numbers are based on a sample size of 450 and will increase if the overall sample size increases.

The initial study drug dose (per dose amount) is based on a tiered, weight-based dosing scheme shown in Table 2.

Table 2. Initial Study Drug (FG-4592 or Placebo) Dosing

Study Drug (Dose Frequency)	Low Weight (<70 kg)	Medium Weight (70 to 100 kg)	High Weight (>100 kg)
FG-4592/Placebo (TIW)	70 mg	100 mg	120 mg

Abbreviations: TIW = three times a week; QW = once a week.

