Appendix 4 Liver Safety Monitoring and Assessment Guidelines

The guidelines described in this section are intended to enable early detection and action following abnormal LFT results and are consistent with FDA guidance for monitoring of Drug Induced Liver Injury (DILI).

It is the responsibility of the Investigator to expeditiously review LFTs, follow these guidelines and contact the Medical Monitor if a study subject meets any of the LFT abnormalities specified below.

In addition:

Repeat LFTs within 2-3 days if:	Discontinue Study Drug, if:

 • ALT or AST > 3x ULN, or • Tbili > 2x ULN 	
 • ALT or AST > 8x ULN, or • ALT or AST > 5x ULN for > 2 weeks, or • ALT or AST > 3x ULN and (Tbili > 2x ULN or INR > 1.5), or • ALT or AST > 3x ULN with appearance of fatigue, nausea, vomiting, right upper quadrant pain or tenderness, fever, rash, and/or eosinophilia (> 5%)

Abbreviations; ALP = alkaline phosphatase; ALT = alanine aminotransferase; AST = aspartate aminotransferase; Tbili = total bilirubin; ULN = upper limit of normal.

Repeat LFTs 2-3 times weekly, then weekly or less until abnormalities stabilize or return to within normal limits. LFTs should include the usual 4: ALT, AST, Tbili and ALP

If close monitoring for LFTs in a subject is not possible, study drug should be discontinued

Evaluate the subject for potential causes, which may include the following:

- Detailed history of symptoms and prior or concurrent diseases
- Concomitant drug use, including nonprescription medications, herbal and dietary supplements, alcohol or recreational drug use, or special diets
- Exposure to environmental chemical agents
- Rule out acute viral hepatitis types A,B,C,D,E; autoimmune or alcoholic hepatitis; nonalcoholic steatohepatitis; hypoxic/ischemic hepatopathy; biliary tract disease
- Obtain additional tests as appropriate: eg, INR, GGT or direct bilirubin; ultrasound or other imaging to assess biliary tract disease
- Consider gastroenterology or hepatology consultations

Once LFTs return to normal, and depending on whether there is an explanation for the LFT elevations, study drug dosing may resume, after discussion with the Medical Monitor

Ref: FDA Guidance for Industry, titled: "Drug-Induced Liver Injury: Premarketing Clinical Evaluations", issued July 2009

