5.4 ADDITIONAL DATA HANDLING RULES AND PRESENTATION SPECIFICATIONS

The following general guidelines will apply to all statistical analyses and data presentations:

- Baseline is defined as the last available value obtained prior to the first dose of study drug, unless otherwise specified in this SAP.
- Hb baseline is defined as the mean of the last four available values obtained prior to the first dose, including the Day 1 pre-dose value.
- eGFR and urine albumin-to-creatinine ratio (UACR) baseline will use the mean of all available central lab values prior to the first dose of study drug, including the Day 1 pre-dose value.
- Baselines for reticulocyte count, reticulocyte hemoglobin content (CHr), hepcidin, hs-CRP, serum iron parameters (transferrin, TIBC, TSAT, Ferritin, sTfR, and iron), blood pressures and heart rate are defined as the mean of values obtained within two weeks prior to the first dose.
- Randomization stratification factors derived from actual data (not the ones from the randomization system) will be used in all applicable analysis models. A table will show the discrepancies between the two.
- Analysis visits (instead of the nominal visits from CRF) derived from visit dates and visit time windows will be used in all analyses, tables, listings and figures. Unscheduled visits within an allowable window will be grouped into the closest scheduled visits based on the visit window specified in Appendix 1. For subjects who have more than one measurement at a scheduled visit, the last measurement will be used, with the exception of CPK, WBC, liver function tests (i.e., ALT, AST, GGT, ALP, and total bilirubin), in which the maximum measurement will be used.

- By default, US conventional units will be used for laboratory value presentations. A set of lab summary tables in SI units will also be provided based on TLF index.
- Age is calculated as of date that the informed consent form was signed.
- age = INTCK('YEAR', Birth Date, Date of Informed Consent, 'C')
where INTCK is a SAS function.
- Duration of treatment or days in treatment is calculated as: last dose date – first dose date +1
- Body weight, height and temperatures will converted using the following formula:
 - kg = lb/2.2
 - cm = 2.54 x in
 - C° = (5/9) x (F° – 32)
- eGFR will be calculated using the following Modification of Diet in Renal Disease (MDRD) equation:

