13.1.1 Proportion of Subjects with TEAE

An AE (classified by preferred term) occurring after the first dose of study medication and up to 28 days after the last dose of study medication will be considered a treatment emergent adverse event (TEAE) if it was not present prior to the first dose of study medication, or it was present prior to the first dose of study medication but increased in severity during the double-blind treatment period. An AE that occurs more than 28 days after the last dose of study medication will not be counted as a TEAE. TEAEs up to 3 days and 7 days after the last dose of study medication may also be evaluated.

The number and percentage of subjects reporting TEAEs in each treatment group will be tabulated by system organ class and preferred term; by system organ class, preferred term, and severity (≥ 3 in a separate table); and by system organ class, preferred term, and Investigator-determined relationship (at least possibly related in a separate table) to study medication. If more than one event occurs with the same preferred term for the same patient, the patient will be counted only once for that preferred term using the most severe and most related occurrence for the summarization by severity and by relationship to the study medication.

The distribution of TEAEs by severity and relationship to study medication will be summarized by treatment group.

The number and percentage of subjects reporting common ($\geq 5\%$ of subjects in any treatment group) TEAEs, treatment-emergent serious AEs (TESAE), renal TESAEs and AEs leading to discontinuation of study medication will be summarized by SOC, preferred term and treatment group, sorted in decreasing frequency overall. In addition, the number and percentage of death and fatal SAEs (i.e., events that caused death) will be summarized by treatment group, SOC and preferred term.

Sensitivity analysis of TEAE during study medication treatment will consist of a summary of TEAE and TESAEs reported after the first dose of study medication up until 72 hours (to cover > 4 half-lives of roxadustat post treatment) and 7 days after the last dose of study medication.

Treatment emergent major cardiovascular events (death, stroke, myocardial infarction) stratified by baseline eGFR (<10 , $10-<15$, $15-<30$, and ≥ 30 mL/min/1.73 m²) will be tabulated.

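### The liver scatter plot and individual liver listing stop at the end of treatment, so a combined enzyme and bilirubin rise completed after permanent discontinuation would be plotted as an isolated ALT or AST rise

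*SAP*

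**What the plan says.** SAP 13.2.1 plans three liver displays and one open-ended listing.

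- A matrix scatter plot of "maximum ALT, AST, ALP and total bilirubin during the treatment period crossed against each other on log scales".
- An individual listing for subjects whose transaminases reach 3 x ULN or whose total bilirubin reaches 2 x ULN. Its time limit is in the closing words of the sentence: "with corresponding other liver enzymes and bilirubin values during the treatment periods will be listed".
- A plot of time to first abnormal liver enzyme or bilirubin, with no window stated.
- A listing of additional information for subjects who need further liver work-up. Neither its content nor its window is stated.

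The SAP does not define where the treatment period ends for laboratory data. The nearest guide is SAP 5.4: "Duration of treatment or days in treatment is calculated as: last dose date" minus first dose date plus one. Protocol 4.1 makes follow-up a separate period: "Post-treatment Follow-Up Period*: 4 weeks".

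Protocol Appendix 4 lists the liver findings on which study drug is discontinued, beginning with "ALT or AST > 8x ULN, or" and continuing with other ALT/AST rules. It then asks sites to "Repeat LFTs 2-3 times weekly, then weekly or less until abnormalities stabilize or return to within normal limits".

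For adverse events, SAP 13.1.1 uses a longer window: "up to 28 days after the last dose of study medication will be considered a treatment emergent adverse event (TEAE".

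**The concern.** A liver scatter plot is read for subjects in whom transaminases and bilirubin are both raised. The two analytes need not peak together, and the protocol stops drug and intensifies testing once transaminases cross a limit. For a permanently discontinued subject, that intensive testing comes after the last dose, where the plot and the listing do not look. A subject whose bilirubin crosses 2 x ULN only then would be placed among the isolated ALT or AST rises. One whose ALT or AST goes on rising would be shown below the true peak.

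The two displays also sit awkwardly with the adverse-event rule. A hepatic event on day 14 after the last dose counts as treatment-emergent, while the laboratory values behind it are outside the liver plot. What is at stake is how reliably a reader can say from these displays whether combined cases occurred, and in which arm.

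**Working it through.** There is no stated figure to reproduce. The check is a comparison of sections.

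**1. Which stopping rules can act without a bilirubin rise (Protocol Appendix 4)?**

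- ALT or AST above 8 x ULN: no bilirubin needed.
- ALT or AST above 5 x ULN for more than 2 weeks: no bilirubin needed.
- ALT or AST above 3 x ULN with symptoms, rash or eosinophilia: no bilirubin needed.
- ALT or AST above 3 x ULN with either bilirubin above 2 x ULN or INR above 1.5: the bilirubin branch already meets the joint criterion at the stop; the INR branch need not.

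**2. Are liver tests planned after the stop?** Yes. Appendix 4 has repeats with no fixed end date. Protocol 7.1.2.6 has early-termination assessments soon after dosing ends. Protocol 7.1.3.1 has a serum chemistry panel 4 weeks after end of treatment or early termination.

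**3. Which of these values do the plot and listing use?**

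| Situation | Outcome in the plot and listing |
|---|---|
| Stopped with bilirubin already above 2 x ULN | Joint elevation is shown |
| Dosing later resumes, as Appendix 4 permits | Values in the gap lie between first and last dose, so they are kept |
| Early-termination draw no more than 7 days off drug | May be kept: SAP Table 17.1-1 maps it to a scheduled visit |
| Permanent stop with no bilirubin rise; bilirubin first reaches 2 x ULN in later repeats or at end of study | Plotted as an isolated ALT or AST rise |
| Permanent stop; ALT or AST peaks in later repeats or at end of study | Plotted peak is too low |

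Only the last two rows are a clear gap.

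**4. Does another planned output show the joint picture?**

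- SAP 17.2 lets every post-baseline value count towards potentially clinically significant (PCS) values and puts every assessment in the data listings. SAP 13.2 adds a listing of PCS subjects and one of their adverse events.
- The PCS limits in SAP Appendix 2 work one analyte at a time: ALT or AST at least 3 x ULN, bilirubin above 1.5 x ULN. The counts do not say whether the same subject had both.
- The additional-information listing might hold the values, but nothing says so.
- No section tabulates combined ALT/AST and bilirubin elevation by arm.

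**5. A worked path.** A subject has ALT above 8 x ULN and bilirubin below 2 x ULN on drug, stops for good, and passes 2 x ULN for bilirubin in repeat tests more than 7 days later. The plot uses the on-drug bilirubin maximum, so the point lies in the isolated-ALT area. The later bilirubin appears in the PCS count (if baseline was not already PCS) and in the data listings. A reader would have to match the two analytes by subject number to see the case.

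**The case against.** The strongest reply is that nothing disappears. Values after the stop feed the PCS counts by arm, the PCS subject listing and the full data listings, and the bilirubin limit used there (1.5 x ULN) is lower than the 2 x ULN in SAP 13.2.1. The subjects concerned are also those most likely to appear in the additional-information listing, which carries no treatment-period limit. At most, one plotted point is misplaced in a descriptive figure.

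Much of this stands. A reader might infer that every test after the end of treatment is excluded from the report, or that a liver signal could vanish altogether. The documents do not support either. The end of the treatment period is undefined for laboratory data, early post-stop draws may be mapped in, resumed dosing keeps the gap values, and SAP 17.2 retains all assessments. Nor do laboratory and adverse-event windows disagree in general. The mismatch concerns these two displays.

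What does not stand is the idea that the other outputs do the same job. Single-analyte counts and listings leave the pairing to hand matching, and the content of the additional-information listing is unspecified. The displays designed to show enzymes and bilirubin together remain silent on the later values.

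**Conclusion.** The point holds in a narrow form. For a subject who stops permanently under a rule that needs no bilirubin rise, and whose bilirubin first reaches 2 x ULN (or whose ALT or AST peaks) in later repeat tests or at the end-of-study visit, the scatter plot would show an isolated or understated rise. The listing would omit the values that complete the picture. No planned by-arm analysis corrects this.

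The size cannot be estimated. A reader might apply an assumed rate of 1 combined case per 1000 to the 300 to 800 roxadustat subjects and obtain 300 x 0.001 = 0.3 to 800 x 0.001 = 0.8 expected cases. That rate is not in the documents. The result would also count all combined cases, not the smaller, unknown share completed only after the stop.

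The conclusion assumes that the treatment period for these displays ends at or near the last dose, which is the plain reading of SAP 5.4 and Protocol 4.1. The efficacy analyses and the Appendix 4 rules are untouched. This is a low-cost improvement to the liver-safety read-out.

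**What to change.** In SAP 13.2.1:

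1. For the scatter plot and the individual listing, use all post-baseline values from first dose through the end-of-study visit and, for subjects in Appendix 4 follow-up, through the last available repeat liver test.
2. State the same window for the time-to-first-abnormality plot, which now has none.
3. Mark each value as on or off drug relative to the last dose.
4. Show local-laboratory repeats in the listing, flagged as local. Protocol 7.4.2 allows local results when central turnaround is too slow, while SAP 5.3 analyses central values only, so a wider date range alone would not bring local repeats into view.
5. Add a by-arm table of subjects with ALT or AST at least 3 x ULN together with total bilirubin at least 2 x ULN, with an on-treatment-only version alongside.

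Copying the 28-day adverse-event window would not be enough. SAP Table 17.1-1 accepts end-of-study visits 15 to 31 days after last dose, so panels on days 29 to 31 would still be dropped, as would later Appendix 4 repeats.

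The cost is a little more programming and one extra table. The protocol already requires the tests. The drawback is that some off-drug values not attributable to study drug will appear; the on/off-drug marking and the on-treatment-only version deal with that. Clinical management does not change.

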13.3 VITAL SIGNS

Blood Pressures and Heart Rate baselines are defined as the mean of values obtained from the last 2 weeks of screening including Day 1 prior to the first dose.

Descriptive statistics for vital signs (e.g., systolic and diastolic blood pressure, MAP, pulse rate, and respiratory rate) and their changes from baseline at each visit and at the end of study will be presented by treatment group.

Vital sign values are potentially clinically significant (PCS) if they meet both the observed value criteria and the change from baseline criteria listed in *Table 13.3 - 1* below. The number and percentage of subjects with post-baseline PCS values will be tabulated by treatment group. The percentages are to be calculated relative to the number of subjects with baseline and at least one post-baseline assessment. The numerator is the total number of subjects with at least one post-baseline PCS vital sign value. Shift tables may be presented. A supportive listing of subjects with post-baseline PCS values will be provided including the patient ID, study center, baseline, and post-baseline values. A listing of all AEs for subjects with PCS vital signs will also be provided.

Table 13.3 – 1. Criteria for Potentially Clinically Significant Vital Signs

Vital Sign Parameter	Flag	Criteria*	
		Observed Value	Change from Baseline
Systolic Blood Pressure (mmHg)	High	≥ 170	Increase of ≥ 20
	Low	≤ 90	Decrease of ≥ 20
Diastolic Blood Pressure (mmHg)	High	≥ 110	Increase of ≥ 15
	Low	≤ 45	Decrease of ≥ 15
Pulse Rate (bpm)	High	≥ 120	Increase of ≥ 20
	Low	≤ 50	Decrease of ≥ 20
Weight (kg)	High	-	Increase of $\geq 10\%$
	Low	-	Decrease of $\geq 10\%$

*Except for body weight, a post-baseline value is considered as a PCS value if it meets both criteria for observed value and change from baseline.

Additional analyses may include but are not limited to subgroup analyses of blood pressure in patients without any change in BP meds during treatment period.

13.4 ELECTROCARDIOGRAM (ECG)

Descriptive statistics for ECG parameters (e.g., Heart Rate, PR interval, QRS interval, QT interval, and QTc interval) at baseline and changes from baseline at each assessment time point will be presented by treatment group. QTc interval will be calculated using both Bazett ($QTcB = QT/(RR)^{1/2}$) and Fridericia ($QTcF = QT/(RR)^{1/3}$) corrections; and if RR is not available, it will be replaced with 60/HR in the correction formula.

ECG parameters values are potentially clinically significant (PCS) if they meet or exceed the upper limit values and changes (where applicable) listed in Table 13.4-1 below. The number and percentage of subjects with post-baseline PCS values will be tabulated by treatment group. The percentages are to be calculated relative to the number of subjects with available non-PCS baseline and at least one post-baseline assessment. The numerator is the total number of subjects with at least one post-baseline PCS ECG value. Shift tables may be presented. A listing for all subjects with post-baseline PCS value will be provided including the patient ID, study center, baseline, and post-baseline PCS values.

In addition, a listing of all TEAEs for subjects with PCS ECG values and a listing of subjects with post-baseline significant ECG abnormalities as reported by the investigators will also be provided.

Table 13.4 - 1. Criteria for Potentially Clinically Significant ECG

ECG Parameter	Unit	Higher Limit
QRS interval	msec	≥ 150
PR interval	msec	≥ 250
QTc interval	msec	> 500; Change from baseline > 60

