9.4.4.4 Electrocardiogram

Descriptive statistics for ECG parameters (eg, Heart Rate, PR interval, QRS interval, QT interval, and QTc interval) at baseline and changes from baseline at each assessment time point and for the maximum and minimum value on treatment will be presented by treatment group. QTc interval will be calculated using both Bazett ($QTcB = QT/(RR)^{1/2}$) and Fridericia ($QTcF = QT/(RR)^{1/3}$) corrections; and if RR is not available, it will be replaced with 60/heart rate (HR) in the correction formula. To assess potentially clinically meaningful ECG abnormalities, the number and percentage of subjects with postbaseline ECG values outside a predefined range or limit of change will be tabulated by treatment group, as well as shift tables for results of ECG interpretation (normal, abnormal not significant, abnormal significant).

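### As worded, SAP 13.4 joins the two QTc limits with *and*, against the protocol's *or*, so a literal program would count only values that meet both

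*SAP*

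**What the plan says.** SAP 13.4 defines a potentially clinically significant (PCS) ECG value in one sentence: "ECG parameters values are potentially clinically significant (PCS) if they meet or exceed the upper limit values and changes (where applicable"). Table 13.4-1 has three rows. QRS and PR each carry one level limit. QTc carries a level and a change in the same cell: "> 500; Change from baseline > 60". No word connects the two.

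The numerator is one count per parameter: subjects with at least one post-baseline PCS value. For the denominator, "The percentages are to be calculated relative to the number of subjects with available non-PCS baseline and at least one post-baseline assessment". The same PCS definition selects the subjects for a listing of PCS values and for a listing of their TEAEs.

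Protocol 9.4.4.4 describes the same tabulation as "the number and percentage of subjects with postbaseline ECG values outside a predefined range or limit of change". Protocol 9.5 says that significant changes to the protocol's analyses will be highlighted in the SAP. SAP 13.4 highlights none.

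**The concern.** A long absolute interval and a large rise are separate QTc safety signals, and the protocol's wording counts each. If the SAP sentence is programmed as it stands, a subject who shows only one of them is not flagged. That subject is missing from the PCS count and, unless another ECG value qualifies, from the PCS listing and the linked TEAE listing as well. A low joint count by arm could then be read as reassurance about either signal, although it measures only their overlap.

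**Working it through.** The documents state no figure on this point, so there is nothing to reproduce. The check is first of the text, then of the possible size.

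**Text, side by side**

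1. SAP 13.4 says limit values *and* changes, where applicable. Only the QTc row has a change limit, so the phrase about changes can refer only to QTc. Followed literally, the rule is QTc > 500 and change > 60.
2. Protocol 9.4.4.4 says range *or* limit of change. Followed literally, either one suffices.
3. SAP 13.3 shows how this SAP writes a joint rule: "Vital sign values are potentially clinically significant (PCS) if they meet both the observed value criteria and the change from baseline criteria". The table footnote repeats it: "a post-baseline value is considered as a PCS value if it meets both criteria for observed value and change from baseline". Section 13.4 has no equivalent wording.
4. SAP 13.5 shows how it writes alternative limits. Excessive hematopoiesis is met by either a rise or a level, and each criterion is analyzed separately. Section 13.4 does not do this either.
5. The denominator requires a non-PCS baseline. A baseline value has no change from baseline, so under a joint rule no baseline QTc could ever be PCS and the restriction would do nothing for that row. Under an alternative rule it can act only through the level limit.

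**Two worked cases under the literal rule**

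- 400 to 480 msec: change = 480 - 400 = 80, above 60. The level of 480 is not above 500. Not flagged.
- 460 to 515 msec: the level of 515 is above 500. Change = 515 - 460 = 55, not above 60. Not flagged.

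Under the protocol's *or*, both are flagged.

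**Possible size (all inputs are assumptions)**

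Let baseline B be normal with mean m and SD s, and change D be normal with mean 0 and SD d, independent of B, with one post-baseline ECG per subject. Then:

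- SD of the post-baseline value = √(s² + d²)
- P(level) = P(Z > (500 - m)/√(s² + d²))
- P(change) = P(Z > 60/d)
- P(both) is the bivariate normal upper tail with correlation d/√(s² + d²)
- P(either) = P(level) + P(change) - P(both)

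Over m = 430-440 and s and d each 20-25 msec, the two ends are:

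| | Most overlap | Least overlap |
|---|---|---|
| m, s, d | 430, 20, 25 | 440, 25, 20 |
| SD of post-baseline value | 32.02 | 32.02 |
| P(level) | P(Z > 2.186) = 1.44% | P(Z > 1.874) = 3.05% |
| P(change) | P(Z > 2.4) = 0.82% | P(Z > 3) = 0.13% |
| Correlation | 0.781 | 0.625 |
| P(both) | 0.38% | 0.079% |
| P(either) | 1.88% | 3.10% |
| Both/either | 20.2% | 2.6% |

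A wider set of 36 settings used baseline mean 420, 440 or 460, baseline SD 25 or 35, change SD 20, 30 or 40, and baseline-change correlation 0 or -0.4. The share of values meeting at least one limit that a joint rule would leave unflagged ran from 60.0% to 99.7%. If the limits are alternatives, that share is zero by definition.

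**The case against.** A reader might infer that the SAP definitely requires both limits. The text does not go that far. The two QTc limits are separated by a bare semicolon, and *and* may only be listing the kinds of limit in the table. Where this SAP wants a joint rule, in 13.3, it says so twice and gives level and change their own columns. The non-PCS-baseline denominator also fits alternative limits better, although it serves the QRS and PR rows too and so is evidence rather than proof. The protocol's *or* points the same way. All of this stands, and it makes the rule ambiguous. It does not remove the problem: the operative sentence still says *and*, nothing in 13.4 says *or*, and programmers work from that sentence.

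A second objection is that QTc safety is reported elsewhere. SAP 13.4 gives descriptive statistics for QTc and its change at each time point, under both corrections, and "a listing of subjects with post-baseline significant ECG abnormalities as reported by the investigators will also be provided"; shift tables may be added. Protocol 9.4.4.4 adds maximum on-treatment values and shifts in ECG interpretation. Protocol 2.5 reports a completed thorough QT study in healthy volunteers without evidence of prolongation. This limits the harm. It does not replace a count by arm, because means can hide outliers and the listing depends on investigator judgment.

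A third is that table specifications sit in a separate document (SAP 1), which may already count each limit. That cannot be excluded, but the SAP should not depend on it.

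**Conclusion.** The point holds as a conflict of wording with a practical consequence. SAP 13.4, followed literally, counts only QTc values that meet both limits. Protocol 9.4.4.4 counts values that meet either, and no change is highlighted. The denominator does not suit a change criterion on either reading.

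The size depends on the reading. If the limits are joint, about 3-20% of values meeting either limit would be flagged under the narrower assumptions, and at most 40% (100% - 60.0%) in the wider set. These are values from one ECG per subject. The SAP counts subjects over several ECGs (Weeks 28, 52 and 76, and end of treatment or early termination), so the percentages illustrate the size and do not predict the table.

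A reader might also conclude that most prolonged QTc values will go unreported or that the QTc safety table will be nearly empty. The documents do not support that. They contain no QTc distribution, the joint reading is not the only one, and the omission would affect the PCS count and its two listings, not all QTc reporting. The correction should be made before database lock, because it is cheap and removes the problem on either reading.

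**What to change.** Reconcile SAP 13.4 with Protocol 9.4.4.4 by splitting the QTc row of Table 13.4-1 into three separately counted rows: QTc > 500 msec; change from baseline > 60 msec; both. Do this for QTcF and for QTcB, since the SAP computes both and does not say which the PCS rule uses.

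Use the non-PCS-baseline denominator for the level row only. For the change row, use all subjects with a baseline and at least one post-baseline ECG. State the denominator of the combined row too. Let a value that meets either limit place the subject in the PCS and TEAE listings. In the same edit, align the sentence's inclusive threshold (meeting or exceeding) with the strict > in the QTc cell.

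The cost is a few extra table rows from data already collected.
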